1.4 Potential Risk and Benefit

1.4.1 Potential Risk

The toxicological profile of PDC-1421 was characterized in single and repeat oral dose studies of up to 13 weeks in rats and repeat oral dose studies of up to 28 days in dogs. Genetic toxicology and safety pharmacology have also been conducted. PDC-1421 was observed to be associated with some adverse effects in serum electrolytes and GI function, but none were clinically significant. Therefore, potential risks of PDC-1421 are fluctuated electrolyte level and gastrointestinal discomfort. We monitored these in the Phase I study and there was no deviation of electrolyte level and no significant gastrointestinal discomfort during monitoring in the clinical trial. However, there were non-clinically significant mild lower diastolic blood pressure and lower heart rate in dog telemetry study and it has been only with the 2500 mg/kg, which is around the NOAEL for dogs. The cardiovascular systems will be monitored in the clinical study.

1.4.2 Potential Benefit

According to nonclinical study results, the results of two *in vitro* assays support the fact that PDC-1421 is a selective norepinephrine reuptake inhibitor and its potency are not inferior to other antidepressants. A TBZ-induced hypothermia study has shown that PDC-1421 is associated with antidepressant activity. Furthermore, PDC-1421 will not pose the adverse effects caused by the molecules which possess anticholinergic or antihistamine activities due to its selectivity on norepinephrine transporter.

1.4.3 Risk Benefit Ratio

Potential risks in nonclinical results outlined above are minor and easy to monitor. Even though there were adverse events in phase I trial, they were no consistent findings in the direction of changes of potential risks in nonclinical studies. Therefore, the subsequent trial could be benefited from the information obtained from this study.

1.5 Dosage Regimen

Based on the FDA's guidance documents, NOAELs from toxicity studies were used to estimate the starting dose in our study. Table 10 summarizes the MRSD for 60 kg human/day calculated from the NOAEL of 28 day repeating dose studies in rats and in dogs using safety margin at 75-fold.

Table 10. Calculation of starting dose

Study	Species	Dosage	HED	Dose for 60 kg human/day
28-day repeated dose subacute oral toxicity study in rats	rat	3000 mg/kg (NOAEL)	483.9 mg/kg	387 mg/day (MRSD)
28-day repeated dose subacute oral toxicity study in dogs	dog	3000 mg/kg (NOAEL)	1666.7 mg/kg	1333 mg/day (MRSD)

Based on these calculations, we proposed the starting dose of PDC-1421 to be at 380 mg/day. In the phase I study, a single dose of PDC-1421 (oral administration) was used to evaluate the safety when taken by healthy subjects. The starting dose and dosage regimen are:

380 mg PDC-1421 (one capsule of PDC-1421 Capsule) once daily after meal.

The dose escalation as follows.

Cohort A (one capsule; 380 mg):

Cohort A enrolled 9 subjects. Seven subjects received PDC-1421 Capsule and two received placebo. There was only one of placebo subjects who met a DLT due to the glucose value at 24 hours after drug administration. We continued the study to the next higher dosage, cohort B.

Cohort B (three capsules; 1140 mg):

Cohort B enrolled 8 subjects. Six subjects received PDC-1421 Capsule and two received placebo. There was only one of placebo subjects who met a DLT due to the glucose value at 4 hours after drug administration. We continued the study to the next higher dosage, cohort C.

Cohort C (six capsules; 2280 mg):

Cohort C enrolled 4 subjects. Three subjects received PDC-1421 Capsule and one received placebo. There was no DLT in this cohort. We continued the study to the next higher dosage, cohort D.

Cohort D (ten capsules; 3800 mg):

Cohort D enrolled 9 subjects. Seven received PDC-1421 Capsule and two received placebo. There is no DLT in the final cohort.

Based on the results, the maximum tolerated dose (MTD) is ≥ 3800 mg of PDC-1421 Capsule so that the safe and well-tolerated for PDC1-421 Capsule is from 380 mg to 3800 mg. According to studies in mouse model system to evaluate efficacious dose, TBZ-induced hypothermia assay, PDC-1421 was indicated to be efficient at 100 mg/kg and 300 mg/kg doses which are equivalent to about 480 mg and 1400 mg in human subjects. We choose 1140 mg (3 capsules), between the efficient dosage, and 2280 mg (6 capsules), above the efficient dosage, which is based on the mice study as the dosage regimen of Phase II trial.

1.6 Compliance with Protocol, Good Clinical Practice (GCP)

and Applicable Requirement

This study and all operating procedures will be conducted in accordance with GCP guidelines, protocol and all applicable regulatory requirements issued by the Minister of Health and Welfare (MOHW) in Taiwan and US FDA, to protect the rights, safety and well-being of the studying subjects.

1.7 Description of the Population to be Studied

We chose patients with major depressive disorder as our subjects in this phase II trial.

2 TRIAL OBJECTIVE

The primary objective of this trial was to determine the effective doses and treatment period of PDC-1421 Capsule in subjects with MDD. The secondary objective was to evaluate the safety of PDC-1421 Capsule in subjects receiving PDC-1421 at various dose levels.

3 TRIAL DESIGN

3.1 General Design

Table 11. Summary of general design

[figure not shown]
	Part I	Part II
Design	Open label, multiple center, dose escalation	Double-blind, randomized, parallel group, placebo-controlled
MDD patients	12	60
Treatment	(1) 1 capsule TID, 6 MDD patients, 28 days (2) Checkpoints (3) If passing the checkpoint: 2 capsules TID, another 6 MDD patients, 28 days (4) Checkpoints	Randomly assigned on a 1:1:1 basis to one of the three arms: (1) 1 PDC-1421 Capsule plus 1 placebo TID (2) 2 PDC-1421 Capsule TID (3) 2 Placebo TID for 42 days
Assessment interval	First week: twice, 3-4 days interval; Once a week during the following second to fourth week	Biweekly
Efficacy and safety evaluation	
• Safety evaluation• Efficacy evaluation	
• Primary endpoint: efficacy measurement (MADRS)• Secondary endpoints: other efficacy and safety measurements (MADRS, DSSS, HAM-D-17,

		HAM-A, CGI, C-SSRS, ECG, vital sign, physical examination, hematology, blood chemistry and concomitant medication evaluation)
--	--	---

The screening phase is intended for diagnosing and assessing the patient for possible inclusion in the study and for providing an adequate washout period. The following study will be conducted in two parts. The targeted population of this study is 72 subjects who met the intent-to-treat (ITT) basis, in which 12 are assigned to part I, 60 are assigned to part II. Part I is an open-label study, multiple center and dose escalation evaluation in twelve patients. Six subjects each will be evaluated for any safety concerns at 1 or 2 capsules TID dose for 28 days, sequentially. Each of them will be assessed twice in the first week after administration of PDC-1421 Capsules and once a week in the following treatment. Part II is a randomized, double-blind, placebo-controlled, parallel-group study. 60 subjects will be randomly assigned on a 1:1:1 basis to one of the three treatment arms (1 PDC-1421 Capsule plus 1 placebo TID, 2 PDC-1421 Capsule TID, 2 placebo TID) for 6 weeks (42 days) and evaluated the safety and efficacy every two weeks during the treatment period. The performance of PDC-1421 Capsule on MDD subjects will provide us with valuable information for our next phase of the study.

Figure 1. General design of procedure

[figure not shown]
Part I.

* Subjects are assessed once between visit 2 and 4

➡ Checkpoints

Part II.

3.2 Primary Endpoint

In part II, the primary endpoint is the change of Montgomery-Åsberg Depression Rating Scale (MADRS) total score from baseline to Week 6 compared to placebo.

3.3 Secondary Endpoint

Table 12 The secondary efficacy endpoints in part II

Number	Items
1	MADRS total score—change from baseline to Visit 3 and 6 (Week 2 and 7).
2	HAM-D-17, CGI, DSSS and HAM-A—change from baseline to Visit 3, 4, 5 and 6 (Week 2, 4, 6 and 7)
3	Percentage of partial responders and responders (defined as participants with a 25-50% decrease and a $\geq 50\%$ decrease from baseline in total score, respectively) in MADRS total score by Week 2, 4, 6 and 7.
4	Safety evaluation—measurements of physical examination, vital signs, laboratory data, ECG, Columbia-Suicide Severity Scale (C-SSRS) and adverse events reports from screening stage to the last visit.
5	Difference in the mean changes of MADRS, HAM-D-17, HAM-A, DSSS, CGI and C-SSRS from baseline to week 2, 4, 6 and 7 between PDC-1421 Capsule and placebo groups.

3.4 Randomization and Blinding

Table 13. Summary of randomization and blinding

	Part I	Part II
Randomization	None (open label)	Randomized; 1 capsule TID: 2 capsules TID: placebo = 1:1:1
Blinding	None (open label)	Double-blind; (1) Unblinding at the end of trial (2) Emergency unblinding at a serious adverse event.

The randomization scheme generated by computer will be prepared by the CRO prior to the start of the study. In part II, subjects will be randomly allocated to the group of one of PDC-1421 Capsule (3 or 6 capsules) or placebo in a ratio of 1:1:1. All subjects and medical staff will be blinded to the treatment assigned till the end of the trial. All emergency unblinding (e.g., due to a serious adverse event) should be reported immediately to the BioLite, Inc. Codes linking randomization number to actual

treatment for each subject will be secured in a sealed, opaque envelop and maintained in the study site and research department of BioLite, Inc.

3.5 Investigational Drug

Investigational drug (PDC-1421 Capsule or placebo) will be maintained and dispensed by the Department of Pharmacy of all clinical sites. No one but the Investigator and/or his/her designee is permitted to access the investigational drug.

3.5.1 Dosage Form and Strength

PDC-1421 Capsule: 380 mg PDC-1421/capsule

Placebo: 380 mg corn starch/capsule

3.5.2 Manufacturer

ITRI (Industrial Technology Research Institute), Hsinchu County, Taiwan

3.5.3 Route of Administration

Oral administration

3.5.4 Dosing Regimen, packing and labeling

Table 14. Summary of dosing regimen

	Part I	Part II
Visits	Once a week (twice in the first week) for 28 days	Biweekly for 42 days
Study drug bags	21 packs for the following week, total 84 packs	42 packs for the following two weeks, total 126 packs
Dosing regimen	Each pack including (1) or (2): (1) 1 capsule of PDC-1421 (380 mg), TID (2) After passing the checkpoint, 2 capsules of PDC-1421 (380 mg), TID	Each pack including (1), (2) or (3): (1) 2 capsules, TID: 1 capsule of PDC-1421 (380 mg) and 1 capsule of placebo TID (2) 2 capsules, TID: 2 capsules of PDC-1421 (380 mg) and 0 capsule of placebo TID (3) Placebo:

		0 capsule of PDC-1421 (380 mg) and 2 capsules of placebo TID
--	--	--

In part I, six subjects each will take 1 or 2 capsules thrice daily for 28 days, sequentially. Subjects are assessed twice in the first week after drug administration and they will receive the study drug bag for the following 7 days every week. In part II, eligible subjects are randomized into one of three treatment arms in a 1:1:1 ratio (one capsule of PDC-1421 Capsule and placebo thrice daily; two capsules of PDC-1421 Capsule thrice daily; two capsules of placebo thrice daily) for 42 days. After the two weeks of drug administration, subjects will return to the center for assessments then get another study drug bag for the following 14 days. The biweekly clinic visits are three times and one week later after the last dose for follow-up.

Investigational drug (PDC-1421 Capsule or placebo) are provided by BioLite, Inc. and stored in Department of Pharmacy of each clinical site. In part I, the first six subjects will take 21 packs with 21 capsules of PDC-1421 Capsule and another six take 21 packs with 42 capsules of PDC-1421 Capsule in every week of trial. In part II, subjects will be dispensed with study drug per 2 weeks which are packaged in a drug bag. A drug bag will contain 42 packs. Depending on the study arms, each pack may contain 2 PDC-1421 Capsules, 2 placebos or 1 PDC-1421 Capsule plus 1 placebo. Each subject will be administered 126 packs in the end of trial. The drug bag of investigational drug is clearly labeled as following:

For Part I-low dose (380 mg TID):

Test Drug: PDC-1421 Capsule

Amount: capsules (reserved capsules included)

Subject Number:

Drug Pack Number:

Study Protocol: BLI-1005-002

Drug Appearance: Brown capsule containing yellow powder

Major Component: Each capsule contains 380 mg of PDC-1421

Dosing: 1 capsule thrice daily after meal for OO days and with extra OO days for reserved

Storage Condition: Store at a dry place at room temperature (15~25°C)

Lot Number:

Manufacturer: Industrial Technology Research Institute

Date of Manufacture:

Date of Expiration:

Sponsor: BioLite, Inc.

Clinical Site: Taipei Veterans General Hospital, Linkou Chang Gung Memorial Hospital and Taipei City Hospital, Songde Branch.

"Caution: New drug - Limited by Federal Law to investigational use".

注意：試驗新藥僅限特定臨床試驗使用

試驗藥物: PDC-1421 膠囊

數量: 顆膠囊 (含 顆備用膠囊)

藥物編號:

受試者編號:

回診次別: Visit

計畫書編號: BLI-1005-002

藥物外觀: 棕色膠囊內含黃色粉末

主成份: 每顆膠囊含有 380 mg PDC-1421

劑量: 三餐飯後服用 1 顆膠囊，OO 日份 (外加 OO 日備用藥)

儲存條件: 儲存於乾燥常溫之環境 (15~25°C)

批號:

製造商: 工業技術研究院

製造日期:

有效日期:

廠商: 萊特先進生醫股份有限公司

試驗機構: 臺北榮民總醫院，林口長庚紀念醫院，臺北市立聯合醫院松德院區

"Caution: New drug - Limited by Federal Law to investigational use".

注意：試驗新藥僅限特定臨床試驗使用

For Part I-high dose (760 mg TID):

Test Drug: PDC-1421 Capsule

Amount: capsules (reserved capsules included)

Subject Number:

Drug Pack Number:

Study Protocol: BLI-1005-002

Drug Appearance: Brown capsule containing yellow powder

Major Component: Each capsule contains 380 mg of PDC-1421

Dosing: 2 capsules thrice daily after meal for 00 days and with extra 00 days for reserved

Storage Condition: Store at a dry place at room temperature (15~25°C)

Lot Number:

Manufacturer: Industrial Technology Research Institute

Date of Manufacture:

Date of Expiration:

Sponsor: BioLite, Inc.

Clinical Site: Taipei Veterans General Hospital, Linkou Chang Gung Memorial Hospital and Taipei City Hospital, Songde Branch.

"Caution: New drug - Limited by Federal Law to investigational use".

注意：試驗新藥僅限特定臨床試驗使用

試驗藥物: PDC-1421 膠囊

數量: 顆膠囊 (含 顆備用膠囊)

藥物編號:

受試者編號:

回診次別: Visit

計畫書編號: BLI-1005-002

藥物外觀: 棕色膠囊內含黃色粉末

主成份: 每顆膠囊含有 380 mg PDC-1421

劑量: 三餐飯後服用 2 顆膠囊，00 日份 (外加 00 日備用藥)

儲存條件: 儲存於乾燥常溫之環境 (15~25°C)

批號:

製造商: 工業技術研究院

製造日期:

有效日期:

廠商: 萊特先進生醫股份有限公司

試驗機構: 臺北榮民總醫院，林口長庚紀念醫院，臺北市立聯合醫院松德院區

"Caution: New drug - Limited by Federal Law to investigational use".

注意：試驗新藥僅限特定臨床試驗使用

For Part II:

Test Drug: PDC-1421 Capsule/placebo

Amount: capsules (reserved capsules included)

Subject Number:

Drug Pack Number:

Visit Number:

Study Protocol: BLI-1005-002

Drug Appearance: Brown capsule containing yellow powder

Major Component: Each capsule contains 380 mg of PDC-1421/placebo

Dosing: 2 capsules thrice daily after meal for 00 days and with extra 00 day for reserved

Storage Condition: Store at a dry place at room temperature (15~25°C)

Lot Number:

Manufacturer: Industrial Technology Research Institute

Date of Manufacture:

Date of Expiration:

Sponsor: BioLite, Inc.

Clinical Site:

"Caution: New drug - Limited by Federal Law to investigational use".

注意：試驗新藥僅限特定臨床試驗使用

試驗藥物: PDC-1421 膠囊/安慰劑

數量: 顆膠囊 (含 顆備用膠囊)

藥包編號:

受試者編號:

回診次別: Visit

計畫書編號: BLI-1005-002

藥物外觀: 棕色膠囊內含黃色粉末

主成份: 每顆膠囊含有 380 mg PDC-1421 或安慰劑

劑量: 三餐飯後服用 2 顆膠囊，00 日份 (外加 00 日備用藥)

儲存條件: 儲存於乾燥常溫之環境 (15~25°C)

批號:

製造商: 工業技術研究院

製造日期:

有效日期:

廠商: 萊特先進生醫股份有限公司

試驗機構:

"Caution: New drug - Limited by Federal Law to investigational use".

注意：試驗新藥僅限特定臨床試驗使用

3.5.5 Study Drug Storage

Investigational drugs will be stored in a locked cabinet at room temperature (15~25°C)

in Department of Pharmacy of each clinical site.

3.6 Premature Termination or Suspension of the Study

The Investigator and/or the Sponsor may decide to stop the trial if:

- Safety assessment clearly indicates that one study arm is associated with more severe or serious adverse experiences.
- The Sponsor decides to terminate the trial if necessary.

4 SUBJECTS SELECTION AND WITHDRAWAL

Inclusion and exclusion criteria in part I and part II are as follows.

4.1 Inclusion Criteria

1. Outpatients aged 20-65 years.
2. Subjects must be able to understand and willing to sign informed consent.
3. Female subjects of child-bearing potential must test negative to pregnancy and use appropriate birth control method from the beginning of study to the 15 days later after ending of study.
4. Met criteria for MDD without psychotic features as defined by the Diagnostic and Statistical Manual of Mental Disorders, Fourth Edition Text Revision® (DSM-IV-TR) and confirmed by use of the Mini International Neuropsychiatric Interview (MINI).
5. 17-item HAM-D (Hamilton Rating Scale for Depression) total score ≥ 20 and CGI (Clinical Global Impression) total score ≥ 4 .

4.2 Exclusion Criteria

1. Have a current or previous major psychiatric disorders which be defined to be per the DSM-IV-TR, including obsessive-compulsive disorder, posttraumatic stress disorder, bipolar I or II, manic or hypomanic episode, schizophrenia, major Axis II disorders which might compromise the study, and major depression with psychotic symptoms, mental retardation.
2. Use of any treatment for MDD in the last 2 weeks before visit 1 (4 weeks for fluoxetine).
3. Use of psychoactive drugs within the last 2 weeks before visit 1 other than that subjects had insomnia who need the treatment as determined by the Investigator.
4. Subjects who were non-responsive to two or more courses of antidepressant medications given an adequate dosage* for symptom treatment within four weeks, or by the judgment of the investigator considered to have treatment resistant depression (TRD), or a history of electroconvulsive therapy (ECT), transcranial magnetic stimulation (TMS) or psychosurgery within the last year.
5. Have a history of any seizure disorder.
6. Any clinically significant abnormal vital sign, ECG, laboratory values as determined by the investigator which might interfere with the study.

7. Any organic disorder caused medical related depression which cannot be under well-controlled such as clinically significant in neurological, gastrointestinal, renal, hepatic, cardiovascular, respiratory, metabolic, endocrine, hematological or other major disorders.
8. Have a high suicidal risk as measured by MINI.
9. Have a history of substance dependence/abuse** within the past 6 months or any positive drug screen result is determined to be caused by subject's drug abuse at visit 1.
10. Have a history of severe allergies to more than 1 class of medication or multiple adverse drug reactions.

* The adequate dosage of the antidepressant medication is defined as the average of the usual dose (mg/day) recommended in American Psychiatric Association (APA) Practice Guideline for the Treatment of Patients with Major Depressive Disorder, Third Edition. E.g. the usual dose of Citalopram is 20-60 mg/day, the adequate dosage is 40 mg/day.

** Tobacco is excluded here, and alcohol abuse is defined as average pure alcohol intake is more than 112 g (for male) or 56 g (for female) per week and/or with Alcohol withdrawal syndrome. Pure alcohol intake =% (Concentration or alcohol content) x c.c. (volume)x 0.79 (density of alcohol). Result of serum ethanol test should be equal to or lower than 10.0 mg/dL to be determined as eligible for the trial. If test result is between 10.1 to 29.9 mg/dL, only one re-test is allowed per subject to meet the criterion. Subject with test result equal to or higher than 30.0 mg/dL is to be excluded.

4.3 Subject Recruitment and Screening

[figure not shown]
At Visit 1, Investigator will introduce the proposed clinical study to subjects who are interesting in this study. If a subject is willing to undergo an informed consent process based on GCP and participate in our study, the subject will be examined as described in section 5.2. At Visit 2, based on Visit 1 measurements, subject who meets the recruitment criteria will be enrolled in this study.

4.4 Subject Identification

In order to protect each subject's privacy, only subjects' initials will be used as part of subjects' identifications. In addition, a subject number will be assigned to each subject who signed the ICF and each subject who is eligible to enroll in the study.

4.4.1 Subject Initial Allocation

A subject's initial will be assigned to each subject by the clinical research coordinator (CRC). Remain blank in the 3rd and 4th space if there have no more initial(s) to be filled in.

English initial of the fourth character in the name

English initial of the third character in the name

English initial of the second character in the name

English initial of the first character in the name

4.4.2 Subject Number Allocation

Each subject will be assigned a number by the CRC. All subject numbers will have six digits.

□□-□□-□□

The fifth and sixth digits: the randomized number will be consecutive numbers commencing with “01”. At screening visit, these should be blank.

The third and fourth digits: the screening number will be consecutive numbers commencing with “01”

The second digit: the site number.

The first digit: the part number; Part I will be assigned to “1”, Part II will be assigned to “2”.

4.5 Early Withdrawal of Subjects

Subjects are not obligated to give reasons for discontinuation from this study. Investigator can ask a subject to be withdrawn from study in the best interest of the subject. Subjects withdrawn from the study due to adverse event(s) must be followed until the events are resolved or stabilized. The discontinuation will result from the following reasons:

- Subjects wish to withdraw.
- Subjects can't obey the regulation of the study.
- Investigator consider that withdrawal from study is the best interest of a subject.
- The subject is pregnant during the trial.

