8.4 Premature Termination and Handling of Missing Data

Any premature termination of the study therapy will be recorded in CRF. Listing of the subjects with premature termination will be provided with the dates and reasons. Missing data caused by premature termination will be utilized the last observation carried forward (LOCF).

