## 5.3 Statistical Methods Planned in the Protocol and Determination of Sample Size

### 5.3.1 Populations for analysis

The efficacy measures are conducted on the per-protocol (PP) and intent-to-treat (ITT) basis. The per protocol will be defined as (1) The drug compliance is at least 80% (2) Subjects have completed data to determine the primary endpoint. (3) Subjects cannot have protocol deviation. The protocol deviation will be defined as (1) Inclusion or exclusion criteria not satisfied. (2) Not permitted concomitant medications (3) Wrong randomized treatment prescribed. An intent-to-treat (ITT) basis will be defined as the data are analyzed by the treatment groups to which the randomized patients who take at least one dose of study medication and have any post-baseline safety data collected.

The safety measures are conducted on the ITT basis.

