### 6.1 Data Sets Analyzed

Two study populations are intention-to-treat (ITT) population and per-protocol (PP) populations which are defined in section 5.3.1.

The efficacy evaluations will be performed on both of the ITT and PP datasets while the safety evaluations will be performed on the ITT dataset. The primary conclusion will be made for the primary endpoint on the ITT population

Demographic and baseline (Visit 2) characteristics will be performed on the ITT population.

Sample size, mean, 95% confidence interval of mean, median, standard deviation, inter-quartile range, maximum and minimum will be summarized for continuous variables. For categorical variables, the frequency and percentage will be provided.

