### ***6.6.2 Handling of Dropouts or Missing Data***

Missing data caused by premature termination will be utilized the last observation carried forward (LOCF). However, the LOCF method will only be applied to data on efficacy. No imputation will be done for safety data.

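### Protocol 4.5 and 8.4 do not separate stopping study drug from leaving the study, and no week-6 MADRS is planned after an early stop, so the primary value for these patients is carried forward

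*Protocol*

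**What the plan says.** **Leaving the study.** Protocol 4.5 speaks of the study, not of the drug: "Subjects are not obligated to give reasons for discontinuation from this study". Its grounds are the subject's own wish, "Subjects can't obey the regulation of the study", the investigator's view of the subject's best interest, and pregnancy. Its one instruction for afterwards is that "Subjects withdrawn from the study due to adverse event(s) must be followed until the events are resolved or stabilized". Section 7.6.1 adds monitoring of serious adverse events. Neither section mentions efficacy assessments after withdrawal.

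**Stopping drug.** Protocol 8.4 says "Any premature termination of the study therapy will be recorded in CRF", asks for a listing with dates and reasons, and continues: "Missing data caused by premature termination will be utilized the last observation carried forward (LOCF"). SAP 6.6.2 repeats the rule and adds: "However, the LOCF method will only be applied to data on efficacy".

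**Visits.** In Table 16 (Protocol 5.2) and SAP 5.2.3, Part II MADRS is taken at Visits 3, 4 and 5 (weeks 2, 4 and 6, each within 2 days) and at Visit 6. Protocol 5.2.3 places Visit 6 one week after the last dose and includes MADRS there. There is no early-termination visit and no instruction for patients off drug.

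**Populations.** Protocol 8.3 and SAP 5.3.1 define ITT as randomised, at least one dose, and some post-baseline safety data. The per-protocol set requires "The drug compliance is at least 80" per cent, complete data for the primary endpoint, and no protocol deviation; prohibited medication counts as a deviation. SAP 6.1 states: "The primary conclusion will be made for the primary endpoint on the ITT population".

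**The concern.** The question is which scores are collected, before any choice of imputation. The primary endpoint is MADRS change to week 6. If a patient who stops drug in week 3 is treated as having left the study, no week-6 score will exist, and the primary analysis substitutes an older one. Depression scores normally move over six weeks, in all arms, so an old score is not a neutral stand-in. If the arms lose different numbers of patients, or lose them for different reasons, the substitution does not cancel in the dose-placebo difference. No later analysis can recover scores that were never taken.

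A second problem follows. Section 4.5 gives a ground for ending participation that could cover poor compliance or prohibited medication, while 8.3 handles those same breaches by exclusion from the per-protocol set only. Two sites could apply these passages differently.

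**Working it through.** The plan states no dropout rate, SD, effect size or power, so there is no figure of its own to reproduce beyond 3 x 20 = 60. Days, sample size and definitions below come from the documents. Rates, gaps and distributions are assumptions.

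**1. What an early stopper contributes at week 6.** Count Visit 2 as day 0 and week 6 as day 42.

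| Last dose | Last treatment-visit MADRS | Age at day 42 | If Visit 6 follows the early last dose |
|---|---|---|---|
| Before Visit 3 | None after baseline | Not defined | Score 7 days after last dose |
| Day 17 | Day 14 | 42 - 14 = 28 days | Day 24; age 42 - 24 = 18 days |
| Day 35 | Day 28 | 42 - 28 = 14 days (12 if Visit 4 was on day 30) | Day 42; age 0 |

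Only a stop near day 35 yields a score at about week 6, and only if Visit 6 is tied to the early last dose. SAP 6.6.9 (relocation of visit data by time window) was not in the text available to me, so I take no view on whether such a score would be assigned to week 6. ITT membership needs safety data, not a post-baseline MADRS, and the sections read here do not say whether LOCF may carry the baseline score.

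**2. Numbers affected.** At 10%, 20% or 30% stopping, 6, 12 or 18 of 60 patients have a carried value and 54, 48 or 42 an observed one.

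**3. Shift in an arm mean.** Shift = proportion stopping x (last score - true week-6 score).

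- Low: 0.10 x 2 = 0.2 MADRS points.
- High: 0.30 x 6 = 1.8 MADRS points.

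The error in the difference is the active-arm shift minus the placebo shift: zero if they are equal, the full amount if only one arm is affected.

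**4. Simulation.** One active arm against placebo, 20 per arm, Wilcoxon rank sum at two-sided 0.05, 3,000 runs (a single comparison, without the Kruskal-Wallis step or Holm). Assumed: SD of change 9, placebo change -10, 45% of the change reached by week 2, correlation 0.7, stopping likelier with poor outcome, week-2 score carried.

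| True difference | Stopping, placebo / active | LOCF estimate |
|---|---|---|
| 0 | equal, 10-30% | about 0 |
| 0 | 10% / 30% | +0.6 |
| 0 | 30% / 10% | -0.6 |
| -5 | equal 10%, 20%, 30% | -4.7, -4.5, -4.1 |
| -5 | 10% / 30% | -3.7 |
| -5 | 30% / 10% | -5.2 |

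With no true effect, rejection under LOCF was 2.9% to 4.4%. With a true difference of -5, power was about 38% with full follow-up and 18% to 38% with LOCF.

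If stopping is instead unrelated to outcome, the gap is 10 x (1 - 0.45) = 5.5 points. At 10% / 30% the spurious difference is then (0.30 - 0.10) x 5.5 = 1.1 points.

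**5. The populations side by side.** SAP 6.3.1 and 6.3.2 count compliance only from first to last dose. A Part II patient who takes all 60 capsules over ten days (6 a day) and then stops is 60/60 = 100% compliant. With no other deviation, only the complete-data criterion can keep that patient out of the per-protocol set. For such patients, ITT against per-protocol compares the carried value left in with the carried value taken out. It says nothing about adherence.

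**The case against.** The strongest reply is that much of this is read from silence. No sentence says that stopping drug ends participation, and none forbids a later MADRS. Section 4.5 never mentions stopping drug, and 8.4 says only that it is recorded and that the resulting missing data are carried forward. Section 8.3 keeps patients with low compliance or prohibited medication in ITT and lists complete endpoint data as a separate per-protocol criterion, so some rule-breakers evidently can have week-6 data. All of that stands. The conflict between 4.5 and 8.3 is therefore an undefined boundary, not a proven contradiction. What remains is that no passage asks for a week-6 MADRS off drug, and 8.4 expects stopping to produce missing data.

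Several stronger readings are tempting and do not hold:

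- A reader might infer that early stoppers drop out of the ITT comparison. They do not; LOCF keeps them in with an imputed score.
- A reader might infer that those affected are exactly the treatment failures. The grounds in 4.5 are mixed, and lack of efficacy is not named.
- A reader might infer that no MADRS at all follows stopping. Visit 6 includes one, and it may fall a week after an early last dose.
- A reader might infer an inflated false-positive rate. The simulation shows none under its assumptions.

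It is also fair that the 0.2-1.8 range multiplies one assumption by another, that its top needs 30% stopping with a 6-point gap, and that the primary test is rank-based. The range describes the reported means, not the test statistic.

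**Conclusion.** The concern holds in a limited form. The protocol does not separate stopping drug from leaving the study and plans no week-6 MADRS after an early stop. For those patients, the primary ITT result rests on LOCF, with a possible exception when Visit 6 happens to fall near week 6. The bias in the dose-placebo difference can go either way and depends on which arm loses more patients. On assumed inputs, an arm mean shifts by 0.2-1.8 points. In the simulation, unequal stopping moved a null difference by about 0.6 points and turned a true -5 into anything from -3.7 to -5.2. None of these inputs comes from the documents. This does not invalidate a 60-patient proof-of-concept trial, but it is worth changing because the remedy is cheap. Separately, 4.5, 8.3 and 8.4 must be reconciled on which breaches end participation; I take no view on what that rule should be.

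**What to change.** **Protocol 4.5 and 8.4.** Distinguish stopping study drug from withdrawing consent for assessments. State that every randomised Part II patient who has not withdrawn consent for assessments is asked to attend the remaining scheduled visits, at minimum Visit 5 (week 6) for MADRS, C-SSRS and adverse-event review. Flag scores taken off drug or on another antidepressant. Reconcile both sections with 8.3 on which breaches end participation. When and why treatment stops is left unchanged.

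**SAP 6.6.2.** State that an observed week-6 score is used whatever the treatment status, that imputation applies only when it is absent, and whether a baseline score may be carried. Report the number of carried-forward values by arm. If collection is already complete, these SAP changes can still be made.

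**Cost.** Visit 5 is already in the schedule. The protocol wording needs an amendment approved under Protocol 10.2 (FDA, MOHW and IRB), with renewed consent if the change is judged substantial. Some patients will decline, and some scores will reflect other treatment; the flag lets the report show those separately.
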